	This study is important because if eventually effective, RLIC could have profound effect on the rehabilitation and recovery of brain plasticity and muscle performance in children with CP and other neurological population.
Study Design	Between groups repeated measures design.
Groups	
Group 1: Children with CP receiving RLIC
 
Group 2: Children with CP receiving sham conditioning
 
Children who qualify and consent will be randomly assigned to either group 1 or 2. Participants will be blinded to the group assignment and the assessor will be blinded to the participant's group assignment.

Number of Subjects & Power Analysis	
Sample size estimates are based on peak knee extension power data from Moreau et al. A total of 24 participants (12 in each group) will provide 80% power to detect an effect size of 0.62 at significance level of 0.05.
 
The sample size was calculated based on a two-sided Wald test of regression coefficients in linear mixed effects model adjusting for design effect and correlation of repeated measures from the same subjects.

Inclusion & Exclusion Criteria	
Inclusion Criteria:
 
 
1. Children diagnosed with unilateral or diplegic CP
 
2. Gross Motor Function Classification System (GMFCS) levels I-III
 
3. 6-13 years of age
 
 
Exclusion Criteria:
 
 
1. Children with other developmental disabilities such as autism, developmental coordination disorders, etc.
 
2. Children with cognitive deficits or communication problem
 
3. Children with balance disorders such as vestibular disorders, posterior fossa tumor etc.
 
4. Children with known cardiorespiratory dysfunctions
 
5. Children who are receiving other adjunct therapies such as TMS, tDCS, vagal nerve stimulation etc.
 
6. Presence of lower extremity condition, injury, or surgery which could compromise conditioning and training
 
7. Children with sickle cell disease
 

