	
Quadriceps power: will be measured using Humac Norm Isokinetic testing device (Computer Sports Medicine Inc, Stoughton, MA). Quadriceps power over 5 maximal test repetitions at 90°/sec will then be calculated every 10 ms (velocity x torque).
 
Electromyography (EMG): The EMG data will be used to quantify the electrical amplitude of quadriceps muscle. Increase in the amplitude of EMG is an indicator of neurophysiological adaptation to strength training. We will simultaneously record the EMG activity of quadriceps muscle while performing isokinetic testing. EMG data will be gathered 6-channel EMG system (Delsys Inc, USA) with the sampling frequency set at 1000 Hz. Surface EMG sensors will be placed at the muscle belly in the direction of muscle fibers, according to surface EMG for non-invasive assessment of muscles (SENIAM) guidelines (http://www.seniam.org). EMG data will be processed off-line in MATLAB R2016a (MathWorks, Natick, MA) with custom-written software using cutoff frequencies of 20 and 500 Hz for lower and upper band-pass, respectively and by averaging by averaging the amplitude of the EMG activation during the middle 3000 ms for each trial.
 
Performance on the standing balance task will be quantified by identifying the number of seconds in a 30-second trial that an individual is able to maintain the platform within <math>\pm 5^\circ</math> of horizontal.
 
Walking Performance:
 
Walking performance will be measured with:
 
 
1. Walking speed: Self-selected and fast walking speeds will be measured using 10-meter walk test. Children will complete three trials at each speed and the average of the respective trials will be considered for analysis. During these tests, children will walk across a GaitRITE digital mat (CIR Systems, Sparta, NJ) and we will quantify walking speed, step length, step width, and cadence.
 
2. Gait analysis: Lower extremity walking kinetics and kinematics will be measured using a 10-camera motion analysis system (Qualisys Inc., Gothenburg, Sweden) sampling at 200 Hz. Specific kinematic variables are hip, knee, and ankle joint angles at midstance, peak hip extension, peak knee extension, and peak ankle plantarflexion during stance phase. Kinetic dependent variables include peak hip, knee, and ankle sagittal plane joint moments and total support moment, and peak positive and negative hip, knee, and ankle sagittal plane joint power.
 
3. Accelerometry: Lower extremity activity will be measured using accelerometers worn on bilateral ankles for 24 hours. Specific accelerometry variable will be number of steps.
 

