21. Hyngstrom, A. S., Murphy, S. A., Nguyen, J., Schmit, B. D., Negro, F., Guterman, D. D., & Durand, M. J. (2018). Ischemic conditioning increases strength and volitional activation of paretic muscle in chronic stroke: a pilot study. *Journal of Applied Physiology*, 124(5), 1140-1147.
22. Bird, S. P., Tarpenning, K. M., & Marino, F. E. (2005). Designing resistance training programmes to enhance muscular fitness. *Sports medicine*, 35(10), 841-851.
23. Cherry-Allen, K. M., Gidday, J. M., Lee, J. M., Hershey, T., & Lang, C. E. (2015). Remote limb ischemic conditioning enhances motor learning in healthy humans. *Journal of neurophysiology*, 113(10), 3708-3719.
24. Christie, A., & Kamen, G. (2010). Short-term training adaptations in maximal motor unit firing rates and afterhyperpolarization duration. *Muscle & Nerve: Official Journal of the American Association of Electrodiagnostic Medicine*, 41(5), 651-660.

25. Carroll, T. J., Selvanayagam, V. S., Riek, S., & Semmler, J. G. (2011). Neural adaptations to strength training: moving beyond transcranial magnetic stimulation and reflex studies. *Acta physiologica*, 202(2), 119-140.

Table 1: Order of the 16 study visits. Testing occurs on Study Visits 1, 15, and 16. Conditioning which involves 5 cycles of 5 minutes of lower extremity peripheral ischemia (or sham), alternating by 5 minutes of no ischemia, occurs on Study Visits 1-14. Training occurs on Study Visits 3-14 (Study Visits 4-14 occur every other business day, excluding weekends and holidays) and includes power, balance and treadmill training.

Assessment s	Visits															
	1 (D1)	2 (D2)	3 (D3 )	4 (D5 )	5 (D7 )	6 (D9)	7 (D11)	8 (D13)	9 (D15)	10 (D17)	11 (D19)	12 (D21)	13 (D23)	14 (D25)	15 (D26 )	16 (4 weeks from visit 15)
Consent/ Demographic details	✓															
Pre-testing	✓															
Conditioning (RLIC/ Sham)	✓	✓	✓	✓	✓	✓	✓							✓		
Training			✓	✓	✓	✓	✓							✓		
Post-testing														✓	✓	✓

\*D= business day

1. Pre-testing includes: Performance on the- 1) Power task, and 2) balance task, and 3) walking task.
2. Training includes: Training on the- 1) Bilateral Knee Extensor Strengthening, 2) Balancing task on the balance board, and 3) Short burst treadmill training.
3. Post-testing includes: Performance on the- 1) Power task, 2) balance task, and 3) walking task.

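### Daily steps, the only walking outcome outside the laboratory, rest on one 24-hour wear per test point; a week of wear after visits 15 and 16 would be a cheap gain in precision

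*Combined protocol and SAP*

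**What the plan says.** Under Outcome Measures, walking performance has three parts.

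- **Walking speed**, from the 10-meter walk test on an instrumented mat: "Children will complete three trials at each speed and the average of the respective trials will be considered for analysis".
- **Gait analysis**: "Lower extremity walking kinetics and kinematics will be measured using a 10-camera motion analysis system".
- **Accelerometry**, from "accelerometers worn on bilateral ankles for 24 hours": "Specific accelerometry variable will be number of steps".

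The first two are laboratory tests. For steps there is no repeat day, no rule on school or non-school days, no valid-wear rule and no averaging.

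The Table 1 caption states: "Testing occurs on Study Visits 1, 15, and 16". Each child therefore gives one 24-hour count per time point. The caption also states: "Training occurs on Study Visits 3-14". The RLIC and Sham Conditioning section ends conditioning at visit 14. Order of Experiment/Study Visits puts visit 15 on the business day after visit 14, and visit 16 four weeks later with no study treatment in between.

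Data Analysis specifies a mixed model ANOVA with pretest, posttest and follow-up as levels of time. The sample size is justified on peak knee extension power: "A total of 24 participants (12 in each group) will provide 80% power".

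**The concern.** A single day's count reflects what the child happened to do that day as well as the child's usual activity. The plan averages repeated trials for walking speed but takes one replicate for steps, although daily activity depends on circumstances that a supervised walk test controls. If the device is fitted at the visit (the start time is not stated), the 24 hours also include a test visit of two to three hours.

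At stake is whether the trial can say anything about walking in daily life. The Behavioral Training section chooses short-burst treadmill training because it resembles how a child walks in the community, and steps are the only outcome that observes this. Avoidable noise makes a null step result harder to interpret. With 12 per arm, extra wear days cost less than extra children.

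**Working it through.** **The plan's own figure.** No power, variance or expected difference is given for steps. The stated 24 participants, 80% power and effect size 0.62 concern knee extension power. Read as a plain two-sample standardised difference, 12 per arm gives 33% power (0.62/√(2/12) = 1.52; 1.52 − 1.96 = −0.44; Φ = 0.33). The stated 80% is reached if the unstated repeated-measures correlation is about 0.80-0.85, or if 0.62 is Cohen's f. The figure is neither confirmed nor refuted, and nothing below depends on it.

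**Inputs.** From the documents: one day at each of visits 1, 15 and 16; 12 per arm. Assumed, not in the documents: single-day reliability R = 0.4-0.7; correlation c of the child's true step level between visits = 0.8-0.9.

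**Formulas**, in units of single-day variance, with k days averaged:

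- Variance of the measured level: v(k) = R + (1 − R)/k
- Reliability of k days: kR/(1 + (k − 1)R)
- Change from baseline, a days before and b after: v(a) + v(b) − 2cR
- Baseline as covariate: v(b) − (cR)²/v(a)

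The standard-error (SE) ratio is the square root of the new variance over the old.

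**Reliability.** Three days: 1.2/1.8 = 0.67 at R = 0.4 and 2.1/2.4 = 0.88 at R = 0.7.

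**Three valid days at the post-test, one at baseline.** v(1) = 1; v(3) = 0.6 (R = 0.4) or 0.8 (R = 0.7).

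| R | c | Change variance, 1 day → 3 days | SE ratio | Baseline-adjusted variance, 1 day → 3 days | SE ratio |
|---|---|---|---|---|---|
| 0.4 | 0.8 | 1.36 → 0.96 | 0.840 | 0.898 → 0.498 | 0.745 |
| 0.4 | 0.9 | 1.28 → 0.88 | 0.829 | 0.870 → 0.470 | 0.735 |
| 0.7 | 0.8 | 0.88 → 0.68 | 0.879 | 0.686 → 0.486 | 0.842 |
| 0.7 | 0.9 | 0.74 → 0.54 | 0.854 | 0.603 → 0.403 | 0.818 |

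The SE falls by 12-17% for the change contrast and by 16-27% with baseline adjustment. The latter is worth about 1.4-1.9 times the sample (1/0.842² = 1.41; 1/0.735² = 1.85).

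**All seven post-test days valid.** v(7) = 0.486 or 0.743. The SE ratio is 0.773-0.841 for change (for example √(0.766/1.28) = 0.773) and 0.640-0.791 baseline-adjusted (for example √(0.356/0.870) = 0.640).

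**Three days at baseline too.** Change variance is 0.56, 0.48, 0.48 and 0.34 in the order of the table, giving ratios 0.612-0.739, a cut of 26-39%. This is available only if the baseline wear precedes randomisation, because conditioning follows at visit 1 and again at visit 2.

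**Power, illustrative only.** For an assumed true difference of 0.62 SD of habitual steps, c = 0.9 and 12 per arm, going from one to three post-test days moves change-score power from 0.13 to 0.17 (R = 0.4) or 0.31 to 0.41 (R = 0.7). Baseline-adjusted power moves from 0.18 to 0.29 or 0.37 to 0.52.

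**Schedule.** D26 is 25 business days after D1, which is five weeks: calendar day 36, the same weekday as visit 1 if there are no holidays. Visit 16 is then day 36 + 28 = 64. Eight weeks is 56 days, so Table 1 already runs past the stated participation period. Seven days starting the day after visit 16 would end on day 71. Seven days after visit 15 end three weeks before visit 16.

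**The case against.** **Size of the noise.** A reader might infer that day-to-day variation swamps any arm difference. The documents do not support that: they give no step variance, reliability or expected difference. At one visit, day-to-day variation exceeds the variation between children only if single-day reliability is below 0.5; at 0.7 it is 30% of single-day variance. This objection stands.

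**Size of the remedy.** For the change contrast in the planned model, extending only the post-tests gains 12-17%, and the illustrative power stays low. The larger gain needs baseline as a covariate, which is not the planned analysis. This stands, so the change of analysis belongs to the proposal and its cost.

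**Feasibility.** A reader might also infer that longer wear conflicts with nothing. It overlaps no conditioning, training or test, but wear after visit 16 runs beyond the last visit and further past the stated participation period. Three days after a Monday or Tuesday visit would contain no weekend day; a seven-day window removes that difficulty. Device return is not described. A 24-hour wear starting at visit 16 already implies some return step, but for visit 15 none can be inferred, since the device could be fitted at visit 14 and collected at visit 15.

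**Comparability.** With all tests on the same weekday, a weekday effect largely cancels within a child. It does not cancel random day-to-day variation. Pairing one weekday at baseline with a week's average afterwards mixes day type into pre-to-post change and makes variance unequal over time. Both apply alike in the two arms, so the arm comparison is not biased, but the baseline may predict less well than assumed and the gain may be smaller.

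**Importance.** Steps are one of many outcomes, and none of the documents makes them primary. This limits the priority of the point, not its direction.

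**Conclusion.** The point holds as a precision improvement. One 24-hour wear per test point is a thin basis for the only walking outcome outside the laboratory, and day-to-day variation may obscure an arm difference with 12 per arm. More post-test days raise precision under every assumption tried; only the amount is uncertain. It rests on the assumed R and c, and on baseline and post-test days being comparable.

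It should not be read as an error in the sample size. The stated power concerns knee extension power, and no power is claimed for steps. Nor would the change guarantee an informative step result, since a moderate difference could still be missed with 24 children.

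**What to change.** 1. After visits 15 and 16, replace the 24-hour wear with seven consecutive days starting the day after the visit. Every child's window then covers weekdays and a weekend whatever the visit weekday.
2. Define the outcome as mean steps per valid day, requiring at least three valid days including at least one non-school day, and state what makes a day valid.
3. For this outcome, compare arms at visits 15 and 16 with the single baseline day as a covariate, in place of the change contrast.
4. Use the same wear length at baseline only if the baseline wear is moved ahead of randomisation.
5. Describe how devices are returned, and reconcile the stated participation period with Table 1, which already places visit 16 beyond it.

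The cost is several more days of wear for the child after each post-test, some non-wear, a device return after the wear, and an outcome-specific analysis statement. No extra visit is needed for testing.

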RLIC and Sham Conditioning	Remote limb ischemic conditioning will be achieved via blood pressure cuff inflation to 20 mmHg above resting systolic blood pressure up to 200 mmHg.  Sham conditioning will be achieved via blood pressure cuff inflation to 25 mmHg on the more involved thigh. Conditioning will involve 5 cycles of 5 minutes blood pressure cuff inflation followed by alternating 5 minutes of cuff deflation. Subjects will be blinded to their group assignment (RLIC or sham conditioning). Conditioning requires 45 minutes. RLIC or sham conditioning will be performed on visits 1-14.

Behavioral Training	
Three tasks will be used for behavioral training on visits 3-14.
 
 
1) Power training task (20-30 minutes)
 
2) Balance training task (15 minutes; rest breaks as needed)
 
3) Treadmill training (15 minutes)
 
 
Power Training: Prior to training and at the beginning of each training week, we will obtain 1 repetition maximum (1 RM) on each leg. 60-80% of the 1 RM will be used as training intensity with progression toward 80% based on that week's 1 RM. Training will involve unilateral and bilateral leg presses (Total Gym GTS, San Diego, CA), 3 times/week for 4 consecutive weeks (12 sessions). Each session will begin with 5 minutes of warm-up exercises. Each participant will perform 6 sets of 5-7 concentric extension contractions with maximum efforts, and with one-three minutes rest after each set.
 
Balance Task: The balance task requires subjects to stand on a movable platform (Stability Platform, model 16030L, Lafayette Instrument) and to keep the platform in a balanced, horizontal position. This task was selected because it can be easily modified to the appropriate level of difficulty in accordance with each subject's motor abilities.
 
Treadmill Training: We will use short burst interval treadmill training. We will use the self-selected and fast walking speeds determined by the 10-meter walk test as the training intensity for the child for each session. Short burst interval training will consist of 30 seconds fast followed by 30 seconds of slow walking. We chose this type of training since it closely resembles the walking performance of a child in the community.

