--	---

Order of Experiment/Study Visits	
This study involves 16 total visits. Participants will be in the study for up to 8 weeks. Please refer to Table 1 for a timeline of study visits.
 
Visit 1: We will provide informed consent and assent and gather demographic data. Next we will perform baseline assessments for the performance on the quadriceps power, EMG, balance, and walking.
 
Then, we will quantify power of bilateral knee extensor by recording peak knee extensors torque and electromyography of bilateral rectus femoris, vastus lateralis, and vastus medialis.
 
Next, we will gather measurements on balance task.
 
Next, we will assess walking performance using 10-meter walk test, 3-D gait analysis, and accelerometry.
 
Subjects will then be randomized to their treatment group. After randomization, subjects will undergo RLIC or sham conditioning (see RLIC and Sham Conditioning for the details). This visit will take approximately: 3 hours.
 
Visit 2: Subjects will undergo RLIC or sham conditioning This visit will take approximately: 1 hour.
 
Visit 3-14: Subjects will undergo RLIC or sham conditioning. Next, behavioral training will commence (power training task and balance training). The order of behavioral training task practice will be randomized. Visits 3-14 will occur every alternate business day. These visits will take approximately: 2-2.5 hours.
 
Visit 15: Subjects will complete post-testing which will include a) quadriceps power; b) EMG; c) balance task, and d) walking performance. Visit 15 will be on the next business day after visit 14. During this visit, participants will not receive RLIC or sham conditioning. This visit will take approximately: 2 hours.
 
Visit 16: Post-test performance assessment on power, EMG, balance, and walking will be performed after 4-weeks from the visit 15. Participants will not receive RLIC or sham conditioning during the follow-up visits. Participants will fill out a survey on the follow-up visit indicating whether they think that they received RLIC or sham treatment. This visit will take approximately: 2 hour.

Data Analysis	
Data will be analyzed using a mixed model ANOVA with time (pretest, posttest, and follow-up) as within subject factor and group (RLIC vs. sham treatment) as between subject factor.

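### No deciding test is named: declare peak knee extension power primary and test it with one baseline-adjusted group contrast, not the group main effect over all three visits

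*Combined protocol and SAP*

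**What the plan says.** In the combined protocol and SAP, the Data Analysis row reads: "Data will be analyzed using a mixed model ANOVA with time (pretest, posttest, and follow-up) as within subject factor and group" as the between-subject factor. No effect, visit, leg or outcome is singled out.

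The Number of Subjects & Power Analysis row gives the only pointers. "Sample size estimates are based on peak knee extension power data", and 24 children (12 per group) "will provide 80% power to detect an effect size of 0.62 at significance level of 0.05". It adds that "The sample size was calculated based on a two-sided Wald test of regression coefficients in linear mixed effects model", allowing for design effect and repeated-measures correlation. It does not give the coefficient tested, the correlation or the scale of 0.62.

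The Outcome Measures row lists quadriceps power, EMG, balance and walking without rank. Power is velocity times torque, computed at 10 ms steps over five repetitions. Under Order of Experiment/Study Visits, "we will quantify power of bilateral knee extensor by recording peak knee extensors torque". Both legs are measured, and no rule reduces these data to one value per child. Testing is at visit 1 (before randomisation), visit 15 and visit 16, four weeks later. No row declares a primary outcome or sets a multiplicity rule.

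**The concern.** A group-by-time layout with a pretest level yields two overall tests for each variable. The group main effect averages over all three visits, including one that treatment cannot have changed. It therefore carries 2/3 of a sustained effect and 1/3 of an effect that is gone by visit 16. The interaction is not diluted in this way, but it has 2 degrees of freedom. A significant result does not say whether RLIC beat sham after training, at follow-up, or only in the change between the two.

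With no deciding test, visit, leg rule or outcome fixed, the analyst can choose after seeing the data. In a trial of 24 children, a positive result reached that way could not be called confirmatory.

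**Working it through.** **Inputs from the plan.** 12 per arm, two-sided 0.05, effect size 0.62, three test visits.

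**Assumptions.** 0.62 is in SD units (d). It applies to whichever single value per child is analysed. The three visits have equal variances and a common correlation r (compound symmetry). The plan gives no r, so I use 0.5, 0.7 and 0.85.

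**The plan's own figure.** A plain two-group t test with d = 0.62 and 12 per arm has 31% power and would need 42 per arm for 80%. The stated 80% is reached if r is about 0.85 for the interaction, if r is about 0.86 for a baseline-adjusted contrast at one visit, or if 0.62 is Cohen's f (d = 1.24; plain t test 83%). The inputs needed to choose between these are not given, so 24 can be neither confirmed nor called wrong.

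**Formulas, with r = 0.7 and a sustained effect (0, 0.62, 0.62).**

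- Main effect: difference (0 + 0.62 + 0.62)/3 = 0.413; variance of a child's mean (1 + 2r)/3 = 0.80; SE = √(2 × 0.80/12) = 0.365; noncentrality 1.13 on 22 df; power 19%.
- Interaction: λ = (12/2) × Σ(m − mean)²/(1 − r) = 6 × 0.2563/0.3 = 5.13; F on 2 and 44 df; power 49%.
- Visit 15 minus pretest, inside the stated three-level model: variance 2(1 − r) = 0.60; SE = √(2 × 0.60/12) = 0.316; noncentrality 1.96 on 44 df; power 48%.
- Visit 15 adjusted for the visit-1 value: residual variance 1 − r² = 0.51, 21 df, averaged over chance baseline imbalance; power 51%.
- Mean of visits 15 and 16, adjusted: residual variance (1 + r)/2 − r² = 0.36, 21 df; power 66%.

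| Test | r = 0.5 | r = 0.7 | r = 0.85 |
|---|---|---|---|
| Group main effect, sustained | 22% | 19% | 18% |
| Interaction, sustained or gone by visit 16 | 31% | 49% | 80% |
| Interaction, half retained | 24% | 38% | 67% |
| Visit-15 contrast in the three-level model | 32% | 48% | 77% |
| Visit-15 contrast, baseline as covariate | 37% | 51% | 77% |
| Mean of visits 15 and 16, covariate, sustained | 52% | 66% | 88% |
| Same, effect gone by visit 16 | 17% | 22% | 35% |

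Against the same contrast in the existing model, the covariate gains about 5 points, 3 points and nothing (76.6% against 77.4% at r = 0.85).

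If 0.62 is Cohen's f and r = 0.7, the interaction has 93–98% power, the adjusted visit-15 contrast 98% and the main effect 58%.

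**False positives for one variable.** Under these assumptions the main effect uses child means and the interaction uses within-child differences, which are independent. The chance that at least one is significant under the null is 1 − 0.95² = 9.75%. Simulation (60,000 runs) gave 9.8% at r = 0.7 and 9.7% at r = 0.85, with each test alone at about 5%.

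**False positives across variables.** Pooling legs and muscles, I count 1 power + 1 EMG + 1 balance + 8 walkway (4 measures × 2 speeds) + 6 kinematic + 10 kinetic + 1 step count = 28. With one test each at 0.05, the chance of at least one false positive is 1 − 0.95²⁸ = 76% if independent, which is implausible here. It is 49%, 33% and 17% at pairwise correlation 0.5, 0.7 and 0.9. For one variable in each of the objective's three domains it is 14% if independent, and 13%, 11% and 8% at those correlations.

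**The case against.** A colleague may say that the interaction is the conventional test in this design, that the sample-size row already points to peak knee extension power, and that both overall tests are valid. Much of this stands. Four stronger readings are tempting, and the documents do not support them.

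- **That the stated ANOVA is invalid or inflates error by itself.** Each test holds 5%. The 10% arises only if either may count, which the plan neither says nor rules out.
- **That the sample-size and analysis rows contradict each other.** A group-by-time ANOVA can be fitted as a linear mixed model. Equally, the sample-size row specifies no baseline covariate, so the model proposed below is an addition to the plan.
- **That remodelling buys much power, or that using the main effect always loses most of it.** The covariate gains little. At r = 0.5 the main effect keeps 22% against 31–37% for the alternatives, which is more than half.
- **That visit 15 and the mean of both legs are the right choices.** For visit 15, "Visit 15 will be on the next business day after visit 14", so it follows the last conditioning closely, and its power does not depend on retention. It has only 5% power for an effect that appears only at follow-up, and the Background stresses retention. For the legs, "Training will involve unilateral and bilateral leg presses", which favours using both. But unilateral CP is eligible and the sham cuff goes on the more involved thigh, so averaging could dilute an effect in one leg.

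Testing is at a set 90°/sec, so peak torque and peak power largely coincide. What remains open there is best versus averaged repetition, and leg.

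**Conclusion.** The point holds as a gap in specification that the choice of model can largely close. The plan names no deciding effect, visit, leg rule or primary outcome, and the choice matters. With a sustained effect of 0.62 SD, power is 22/19/18% for the main effect against 31/49/80% for the interaction at r = 0.5/0.7/0.85. The false-positive rate is about 10% per variable if either overall test may count. These figures rest on compound symmetry, an assumed r and the SD-unit reading of 0.62. If 0.62 is Cohen's f, power is higher throughout, but at r = 0.7 the main effect still trails badly (58% against 93–98%).

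The sponsor should act on this, chiefly for pre-specification and an interpretable answer. It is not evidence that the stated tests are invalid or that 24 is the wrong number.

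**What to change.** Replace the Data Analysis sentence with the following:

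1. Peak knee extension power is the primary outcome.
2. The model is a linear mixed model with visits 15 and 16 as outcomes, the visit-1 value as covariate, and group, visit and group × visit. It uses small-sample degrees of freedom: a statistic on 21 df compared with 1.96 rejects 6.3% of the time under the null.
3. One group contrast from that model is the single deciding test. The sponsor chooses visit 15, visit 16 or their mean. The mean beats visit 15 only if roughly 65–75% or more of the effect is expected to last.
4. One rule gives one value per child (leg or combination of legs; best or averaged repetition). Both choices are fixed before unblinding.
5. All other outcomes are labelled secondary or exploratory. Any secondary meant to support a claim needs a stated multiplicity rule, such as Holm over a short list.

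If the three-level model is kept, name one group × time contrast, or the interaction, in peak knee extension power as the deciding test, and exclude the main effect.

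The cost is wording only, with no new data, visits or children. The downsides are one error degree of freedom, less sensitivity to time patterns other than the one named, and fewer outcomes able to carry a claim. The change does not guarantee the stated 80% power. For that, the sponsor would need to state the coefficient, the correlation and the scale behind 0.62.
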